## 2.6 Study Center Considerations in the Data Analysis

Up to 10 Centers which include sites in the US, UK, and EU. Analysis will be conducted on the pooled data from all study centers.

## 2.7 Documentation and Other Considerations

The data analyses described in this SAP will be conducted using SAS® Software, version 9.4 or later.

## 3.0 Analysis of Baseline Patient Characteristics

Baseline and demographic characteristics of the safety population will be summarized. Continuous variables (age, height, and weight) will be summarized via mean, standard deviation, minimum, maximum, and number of non-missing responses. Categorical variables (gender, race, and ethnicity) will be summarized via counts and percentages.

A detailed listing of baseline data for each patient in the safety population will also be provided, as shown in Appendix B.

## 4.0 Analysis of Efficacy

### 4.1 Description of Efficacy Variables

#### 4.1.1 Primary efficacy variables

The primary efficacy variables for this study are:

- Tc 99m tilmanocept uptake values ( $TUV_{joint}$ ) for the biopsied joints;
- IHC assessment of macrophage expression of the CD206 receptor.

The primary endpoint is:

- The correlation between joint-specific tilmanocept uptake value ( $TUV_{joint}$ ) and the number and area fraction of CD206 expression as determined by IHC assessment.

#### 4.1.2 Secondary efficacy variables

The secondary variables for this study are:

- IHC and immunofluorescence assessment of macrophage expression and co-expression of the CD68 and CD163 receptors.
- Pathotype classification of RA disease as lympho-myeloid, diffuse myeloid, or pauci-immune fibroid, based on  $TUV_{joint}$ .

The secondary endpoints are:

- The correlation between  $TUV_{joint}$  and the number and area fraction of CD68 and CD163 determined by IHC assessments.
- Classification of synovial anatomic pathology into Lympho-myeloid, Diffuse myeloid, and Pauci-immune fibroid types as a function of CD68, CD163, CD206, CD3, CD20, CD55, and TE7 expression determined by

- IHC assessments using a multinomial logistic regression model with  $TUV_{joint}$  as a covariate.
- The correlation between the expression of CD68, CD163, and CD206.

#### 4.1.3 Exploratory efficacy variables

The exploratory variables for this study are:

- IHC assessment of macrophage expression of the CD3, CD20, CD55, and TE7 biomarkers.
- mRNA levels in synovial tissue for the CD206, CD163, and CD68 biomarkers.
- Flow cytometry measurements of CD206, CD163, and CD68 biomarker expression and co-expression.
- Tc 99m tilmanocept global uptake values ( $TUV_{global}$ ) per subject.
- IHC assessment of the expression of a biomarker (e.g., CD206, TE7) is determined from immunofluorescent microscopy, specifically:
  - The ratio of the total fluorescent stained area to the total field area under 4x and 10x power magnification.
- Pathotype classification of RA disease as lympho-myeloid, diffuse myeloid, or pauci-immune fibroid, based on  $TUV_{global}$ .

The exploratory endpoints for this study are:

- The correlation of the expression of CD3, CD20, CD55, and TE7 with CD206 as measured through IHC.
- The correlation of  $TUV_{joint}$  with the expression of CD206, CD163, and CD68 as measured through RNA-seq.
- The number and size of CD206, CD163, and CD68 expressing macrophages as measured through (optional) flow cytometry and their correlation with  $TUV_{joint}$ .
- The correlation between  $TUV_{global}$  and synovial anatomic pathology as determined by IHC assessments.
- Classification of synovial anatomic pathology into Lympho-myeloid, Diffuse myeloid, and Pauci-immune fibroid types using a multinomial logistic regression model with  $TUV_{global}$  as a covariate.

#### 4.2 Analysis of Efficacy Variables

All efficacy analyses will be conducted on both the ITA and PP populations. The ITA population will be the primary analysis set.

#### 4.2.1 Primary Efficacy Variables

The primary endpoint will be analyzed by computing the Pearson (product-moment) and Spearman (rank) correlation coefficient between the TUV for the biopsied joint and the final CD206 expressing macrophage count. The CD206 expressing macrophage count is derived from the IHC histopathology and ultrasound imaging:

- The fraction of CD206 expressing macrophages under 4x and 10x power magnification, defined as the ratio of the total fluorescent stained area to total field area. Specifically, area fraction (AF) is defined as

$$AF = \frac{\text{Total Stained Area}}{\text{Total Field Area}} \times 100\%.$$

- The volume of synovial tissue in the biopsied joint, defined as the ultrasound synovial thickness score (Vol). The CD206 macrophage count will be the product of these 2 variables (that is, CD206 = AF\*Vol).

CD206 expressing macrophage fraction and TUVjoint will be summarized with descriptive statistics (number of data pairs, means, standard deviations, minima, medians, and maxima as well as the Pearson correlation between the variables). The ultrasound synovitis score will be summarized with a frequency table. Defining  $\rho$  to be the population correlation coefficient, a test of the hypotheses

$$\begin{aligned} H_0: \rho &\leq 0 \\ H_a: \rho &> 0 \end{aligned}$$

will be performed using Fisher's Z-transformation and its Normal approximation. A 95% confidence interval for the population correlation coefficient ( $\rho$ ) based on the Fisher Z-transformation (the inverse hyperbolic tangent) and its normal approximation will be provided. The joint distribution of the CD206 macrophage count and TUVjoint will be summarized graphically with a scatter diagram of the data pairs with the least-squares regression line superimposed on the graph. The joint distribution of the component variables of CD206 macrophage count will be graphically summarized with box plots showing the conditional distribution of TUVjoint for each category of synovitis score.

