Planned study dates	Start of study recruitment / February 2021	End of Recruitment/ December 2023 End of Study/ March 2024
Planned number of study centers	Up to 10 centers which include sites in the US, UK, and EU	
Sample size	Approximately 12 to 24 joints (final number based on an interim analysis and adaptive design)	
Justification of sample size	The proposed sample size is sufficient to provide an acceptable standard error (approximately 0.15) on the Fisher Z scale and yield an acceptable confidence interval width on the population correlation.	
Primary endpoint	
• The correlation between joint-specific tilmanocept uptake value (TUV_{joint}) and the number and area fraction of CD206 expression as determined by IHC assessment.	
Secondary endpoints	
• The correlation between TUV_{joint} and the number and area fraction of CD68 and CD163 determined by IHC assessments.• Classification of synovial anatomic pathology into
• Lympho-myeloid• Diffuse myeloid• Pauci-immune fibroidtypes as a function of CD68, CD163, CD206, CD3, CD20, CD55, and TE7 expression determined by IHC assessments using a multinomial logistic regression model with TUV_{joint} as a covariate.• The correlation between the expression of CD68, CD163, and CD206.	

Exploratory endpoints	
• The correlation of the expression of CD3, CD20, CD55, and TE7 with CD206 as measured through IHC.• The correlation of TUV_{joint} with the expression of CD206, CD163, and CD68 as measured through RNA-seq.• The number and size of CD206, CD163, and CD68 expressing macrophages as measured through (optional) flow cytometry and their correlation with TUV_{joint}.• The correlation between TUV_{global} and synovial anatomic pathology as determined by IHC assessments.• Classification of synovial anatomic pathology into Lympho-myeloid, Diffuse myeloid, and Pauci-immune fibroid types using a multinomial logistic regression model with TUV_{global} as a covariate.
Safety Evaluations	Adverse events, clinical laboratory results (hematology, serum chemistry, vital signs, ECG)

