driven RA pathotype and/or with high densities of macrophages in their inflamed synovium respond best to anti-TNF α biologic therapy (Wijbrandts 2008, Dennis 2014), whereas patients with a fibroid pathotype do not respond significantly to anti-TNF α therapy. Although these results need to be confirmed and elaborated upon in further studies, they suggest that determination of the density of activated macrophages in the inflamed synovial membranes of patients with RA could facilitate identification of those RA patients who would most benefit from anti-TNF α therapy and/or those who would not receive benefit. Additional work in this field seeks to determine if similar associations between the efficacies of other treatments and synovial pathotypes can identify those treatments that are most effective in patients with lympho-myeloid and/or fibroid RA pathotypes. Such results, if attained, would provide a great benefit to RA patients by enabling personalized delivery of optimal treatments to all RA patients. The study to be conducted (NAV3-32) is designed to establish the correlation between Tc 99m tilmanocept localization to RA inflamed joints and the number and density of CD206 expressing cells (i.e., macrophages) in the inflamed joints as determined by IHC evaluations of synovial biopsy specimens. If this study is successful, Tc 99m tilmanocept imaging may be able to discriminate the fibroid pathotype from the myeloid and lymphoid pathotypes and may be able discriminate all 3 pathotypes from each other.

Previously generated results from clinical imaging studies conducted by Navidea and extensive peer reviewed scientific literature strongly indicate that Tc 99m tilmanocept can enable non-invasive imaging of aggregates of CD206-expressing cells associated with various pathologies using planar scintigraphy. While it has been suggested that synovial biopsy and IHC evaluations might be translatable to common rheumatological clinical practice, there are 5 reasons why quantitative assessment of CD206 positivity enabled by Tc 99m tilmanocept imaging may be preferred to synovial biopsies for evaluations of RA patients.

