3.2 Justification for Study Design and Population

This study is designed to evaluate the correlation between TUV_{joint} and the number and area fraction of CD206 expression as determined by IHC assessment in the synovium of subjects clinically diagnosed with RA who are not receiving anti-rheumatic treatment or who are on stable anti-rheumatic treatment. The ability of Tc 99m tilmanocept imaging to detect and discriminate RA pathotypes is being evaluated in these subjects with the goal of supporting personalized therapy. A complete rationale for evaluating Tc 99m tilmanocept in this subject population is discussed in [Section 1.1](#).

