8.5 Synovial Biopsy

8.5.1 Joint Selection

All subjects will undergo a synovial biopsy of a selected hand or wrist joint. All joints selected for biopsy will be required to have an ultrasound gray-scale synovitis score of ≥ 2 (range 0 to 3). In instances where more than 1 joint is qualified for biopsy, the candidate joint will be selected based on TUV_{joint} (as described in [Table 4](#)).

Table 4 Biopsy Selection Options

Option	Description
1	The subject has only 1 MCP joint or wrist joint with an ultrasound gray-scale synovitis score of ≥ 2 . This joint will be selected for biopsy.
2	The subject has 2 or more MCP and/or wrist joints with an ultrasound gray-scale synovitis score of ≥ 2 . The joint for biopsy will be selected based on evaluation of corresponding TUV_{joint} . In the first subject with multiple qualifying joints, the joint with the highest TUV_{joint} will be selected; in the second subject with multiple qualifying joints, the joint with the lowest TUV_{joint} will be selected. Selection will proceed in this fashion, alternating between highest and lowest TUV_{joint} .

The ultrasound assessment for synovitis score should take place at screening and prior to biopsy at Visit 4 (Day 3 to 7 post-Tc 99m tilmanocept administration) in accordance with institutional standard operating procedures (SOPs).

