**Table 1 Biopsy Selection Options**

Option	Description
1	The subject has only 1 metacarpophalangeal (MCP) joint or wrist joint with an ultrasound gray-scale synovitis score of $\geq 2$ . This joint will be selected for biopsy.
2	The subject has 2 or more MCP and/or wrist joints with an ultrasound gray-scale synovitis score of $\geq 2$ . The joint for biopsy will be selected based on evaluation of corresponding TUV joint . In the first subject with multiple qualifying joints, the joint with

	the highest TUV joint will be selected; in the second subject with multiple qualifying joints, the joint with the lowest TUV joint will be selected. Selection will proceed in this fashion, alternating between highest and lowest TUV joint .
--	--

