### Calculating Global TUV

For each independent blind reader, determine the average  $TUV_{joint}$  and 95% prediction interval of both the anterior and posterior views of the wrists, MCPs, and PIPs in healthy individuals. For all following calculations, reader specific average  $TUV_{joint}$  and 95% prediction intervals will be used.

For each RA subject do the following.

**Step 1:** Calculate  $TUV_{joint}$  for each of the 22 DAS28 joints for which data are collected.

*Step 2:* Identify all imaged joints with  $TUV_{joint} >$  upper limit of normal for the anatomically similar joint and view. These will be referred to as inflamed joints (IJ). Each joint has an anterior and posterior view: a joint is considered an IJ if either view has a  $TUV_{joint}$  higher than the upper bound from the normative data set.

*Step 3:* Calculate the macrophage-involved contribution (MI) to  $Tc\ 99m$  tilmanocept localization for each IJ. This is done by expressing the TUV for the IJ as a fractional change from the mean TUV for the anatomically equivalent joint and view. That is, if  $TUV_{joint}$  and  $\bar{H}_{joint}$  represent the joint and view specific TUV and the mean TUV for the anatomically equivalent joint and view from the normative data set respectively, the macrophage contribution to TUV is  $MI_{joint}$ :

$$MI_{joint} = \frac{TUV_{joint} - \bar{H}_{joint}}{\bar{H}_{joint}}.$$

*Step 4:*  $TUV_{global}$  is the total of the macrophage-involved contributions for the IJs. (Note that  $MI_k$  is effectively 0 if  $TUV_{joint}$  is less than or equal to the upper limit of normal from the normative data set.) That is,

$$TUV_{global} = \sum_{\text{All IJs}} MI_{IJ},$$

$$TUV_{global} = \sum_{k=1}^{22} MI_k.$$

It is presumed that the presence of radiotracer uptake for a joint indicates the presence of activated macrophages. The use of the term “localization” is synonymous with radiotracer uptake.

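### Does the confidence interval for the primary correlation need changing because the biopsied joint is chosen by its TUV?

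*SAP*

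**What the plan says.** **Analysis.** SAP 4.2.1, following Protocol 9.5.3.1, correlates TUV of the biopsied joint with the CD206 count (area fraction times synovitis score). It gives "A 95% confidence interval for the population correlation coefficient" by Fisher's Z. The SAP adds a one-sided test of ρ ≤ 0 and prints no alpha.

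**Which joint is biopsied.** If only one MCP or wrist joint has a gray-scale score of 2 or more, that joint is taken. With two or more, SAP Table 1 says "The joint for biopsy will be selected based on evaluation of corresponding" TUV_joint. The first such subject gives the highest, the second the lowest, and Protocol 8.5.1 continues: "Selection will proceed in this fashion, alternating between highest and lowest" TUV_joint.

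**Scope of the claim.** SAP 4.1.1 defines the primary variable as TUV_joint "for the biopsied joints". Protocol 1.1 says the study "is designed to establish the correlation between Tc 99m tilmanocept localization to RA inflamed joints" and CD206-expressing cells in biopsy specimens. Protocol 3.2 describes CD206 expression "as determined by IHC assessment in the synovium of subjects clinically diagnosed with RA". The Protocol Synopsis justifies the sample size as enough to "yield an acceptable confidence interval width on the population correlation".

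**Outputs.** SAP 2.5 calculates TUV_joint "for each of the 22 DAS28 joints for which data are collected". Data Listing 25 shows TUV by region of interest without marking the biopsied joint, and Data Listing 27 has no joint column. No other listing gives the biopsied joint, the selection option or the ultrasound score by joint.

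**The concern.** Taking extremes of X usually widens the spread of X, and a wider spread raises a correlation even when the underlying relation is unchanged. Here X is TUV_joint, and the rule takes its extremes within each multi-joint subject. An r from such a sample can exceed the r for a randomly chosen inflamed joint.

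SAP 4.2.1 does not link ρ to the rule, and Protocol 1.1 and 3.2 invite the broader reading. The correlation is the primary endpoint and its size matters, not only its sign. If r were taken to hold for all inflamed joints, it could be overstated and its interval could miss that wider target too often. Without a listing flag, a reader could not trace the analysed pair to a joint.

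A side question concerns the Spearman limits. The footnotes to SAP Tables 4 and 28 name the Fisher Z method with no standard error, and 1/√(N−3) gives limits that are somewhat narrow for a rank correlation when the association is strong.

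**Working it through.** **The plan's own figure.** The Synopsis gives a standard error of about 0.15 on the Fisher Z scale. With SE = 1/√(N−3), N = 12 gives 1/√9 = 0.333 and N = 24 gives 1/√21 = 0.218. An SE of 0.15 needs N = 3 + 1/0.15² = 47.4, about 48. The figure does not reproduce at 12 to 24 joints. That is a separate matter and does not bear on joint selection. The intervals below use the actual N.

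**Planned precision at r = 0.5** (tanh⁻¹ 0.5 = 0.549):
- N = 24: 0.549 ± 1.96 × 0.218 gives 0.12 to 0.75.
- N = 12: 0.549 ± 1.96 × 0.333 gives −0.10 to 0.83.

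**Inputs not in the documents, therefore assumed:** the within-patient correlation of TUV (ICC), the true ρ, the number k of qualifying joints, and the share of single-joint subjects. Under Table 4 the ceiling for k is 10 MCP + 2 wrists = 12.

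**Direction, in closed form.** Assume normal TUV, one linear relation in all joints, and every subject with k joints. The variance ratio of selected to random joints is v = ICC + (1 − ICC)·m, where m is the mean square of the largest of k standard normals. The selected-joint correlation is ρ√v / √(1 − ρ² + ρ²v). With ICC = 0.3 and ρ = 0.5:

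| k | m | v | r, selected joints |
|---|---|---|---|
| 2 | 1.00 | 1.00 | 0.50 |
| 3 | 1.28 | 1.19 | 0.53 |
| 5 | 1.80 | 1.56 | 0.585 |
| 8 | 2.40 | 1.98 | 0.63 |

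At k = 2 there is no distortion. Half the subjects give the larger of two joints and half the smaller, which restores the original distribution.

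**Size, by simulation.** 10,000 trials per cell, 25% single-joint subjects, the rest alternating, N = 24. All-joint truth = ICC × between-patient + (1 − ICC) × within-patient correlation. Entries are selected-joint minus all-joint correlation, then coverage of the all-joint value.

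| Association | k = 2 | k = 4 | k = 8 | k = 12 |
|---|---|---|---|---|
| Equal, ρ 0.5, ICC 0.3 | 0.00; 95% | +0.05; 94% | +0.11; 88% | +0.14; 83% |
| Equal, ρ 0.7, ICC 0.3 | 0.00; 95% | +0.04; 92% | +0.09; 82% | +0.11; 74% |
| Mainly within (0.2/0.8), ICC 0.5 | 0.00; 95% | +0.07; 92% | +0.15; 81% | +0.18; 71% |

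With association mainly between patients (0.8/0.2, ICC 0.5) the difference lies between 0.00 and −0.02 and coverage is 95% at every k. At N = 12 the lowest coverage in any case is 84%.

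- With a mix of 2 to 4 joints in one trial, the difference is −0.01 to +0.04 and coverage 94 to 95%.
- For equal association, ρ = 0.5 and 4 joints, raising the single-joint share from 25% to 50% and 75% cuts the difference from +0.05 to +0.03 and +0.02.
- Multiplying area fraction by a score of 2 or 3, as the endpoint does, gives a similar picture: 0.00 at 2 joints, +0.04 to +0.06 at 4, and +0.11 to +0.16 at 12.

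**Validity for the joints analysed.** Coverage of the selected-joint correlation is 94.5 to 96.6% in all 72 cells. At ρ = 0, one-sided rejection is 2.4 to 2.8% at a nominal 2.5% (assumed).

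**What the rule gains.** In a second set of simulations (20,000 trials per cell, no single-joint subjects, ICC 0.3, ρ = 0.5, N = 24), one-sided rejection at an assumed 5% is 82.5% with one random joint and 94.6% with selection among 5. At N = 12 the figures are 53.7% and 71.0%.

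**Spearman limits, random sampling, N = 24.** At ρ = 0.5, 0.7, 0.8 and 0.9, coverage is 94.2, 93.8, 93.0 and 91.7% with 1/√(N−3). With √((1 + r²/2)/(N−3)) it is 95.5, 95.8, 95.7 and 95.3%. Up to ρ = 0.7 the two err by similar amounts in opposite directions.

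**The case for a change.** The best case for acting is that the size of r is the result the sponsor wants, that Protocol 1.1 presents the agent as assessing all joints, and that k may reach 12. At 8 to 12 joints with equal or mainly within-patient association, the interval would miss the all-joint value in 12 to 29% of trials at N = 24. The remedy looks cheap: one sentence and a few listing columns.

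The factual part stands. SAP 4.2.1 and the Table 4 footnotes do not point to the selection rule, and no listing flags the biopsied joint.

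The rest carries less weight. Including the between-patient case, the miss rate at 8 to 12 joints is 5 to 29%. The upper end needs every multi-joint subject to have that many joints at gray-scale 2 or more, which nothing in the documents suggests. The remedy would leave r, its interval and the test as they are. With one biopsied joint per subject, extra listings could show how far the TUV range widened, but could not separate between-patient from within-patient association.

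Nor is it quite free. Protocol 3.3 requires a formal amendment for changes that are not purely administrative, and SAP Appendix A provides for charges on table changes after approval. Ultrasound is done at two visits, so the qualifying set would first need defining.

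**Conclusion.** No change is called for. This is a missing cross-reference that analysts and report authors can fill. The primary variable is defined on biopsied joints, the same SAP prints the selection rule, and ρ is the ordinary name for what r estimates. The programmer must identify the biopsied joint to compute r at all, so the link will exist in the analysis data even though Data Listing 25 does not display it.

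The interval and the test are sound for joints chosen by the rule. Extrapolated to all qualifying joints, r would be off by −0.02 to +0.07 with 2 to 4 joints per subject, small against an interval at r = 0.5 whose width is 0.75 − 0.12 = 0.63 at N = 24. It could be off by up to +0.18 at 12 joints. These figures assume exchangeable joints, the stated ICCs and correlations, and 25% single-joint subjects. Some loss of generality in return for a wider TUV range and more power in a study of 12 to 24 joints is a fair trade-off, although the documents do not give that as the reason for the rule. The report should say that r describes joints selected by SAP Table 1.

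The Spearman formula does not alter this. The shortfall is about 1 point up to ρ = 0.7, and a clear gain from the alternative appears only at about 0.8 and above.

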#### 4.2.2 Secondary Efficacy Variables

Co-expression of the CD68, CD163, and CD206 markers will be analyzed by 2 methods. First, by providing the product-moment and Spearman rank correlation matrices of the IHC field measurements (that is, the fraction of macrophages expressing the markers will not be multiplied by the synovitis score). Descriptive statistics of the data triplets used to calculate the correlation matrices will be

provided (number of data triplets, means, standard deviations, minima, medians, and maxima). In the second method, histological sections will undergo immunofluorescent staining for the 3 markers and DAPI. For each section evaluated, up to 50 cells from the synovial sublining will be identified for each of the 3 markers. For each identified cell (up to 150/section), the rate of co-expression of the 3 markers will be determined. For sections with sparse marker expressing cells, four microscope fields will be randomly selected. Co-expression of the markers will be quantified for any cell observed expressing a marker.

The ability of  $TUV_{joint}$  to discriminate among lympho-myeloid, diffuse myeloid, and pauci-immune fibroid RA disease types will be evaluated with a multinomial logistic regression model. The model in terms of the logit (log odds) of the outcome is defined as:

$$\ln \frac{\pi_j}{1 - \pi_j} = \alpha_j + \beta_j X$$

where

$j$  = category of the outcome

$\frac{\pi_j}{1 - \pi_j}$  = odds

$\alpha$  = intercept

$\beta$  = slope

$X = TUV_{joint}$

RA type will be the response variable and  $TUV_{joint}$  will be the explanatory variable. ROC curves will be generated using the lympho-myeloid type as the base class. The marginal distribution of disease type will be summarized with a frequency table, while the marginal distribution of  $TUV_{joint}$  will be summarized with descriptive statistics (number of data pairs, mean, standard deviation, minimum, median and maximum). The joint distribution will be graphically summarized with box plots showing the conditional distribution of  $TUV_{joint}$  for each disease type.

